**PROTOCOL TITLE: Efficacy of superior laryngeal nerve block for chronic cough****PRINCIPAL INVESTIGATOR: [name]****1.0 Objectives / Specific Aims**

**AIM:** Determine the overall efficacy of superior laryngeal nerve blocks for the treatment of neurogenic chronic cough. This is the primary aim of the study: to test the hypothesis that superior laryngeal nerve blocks are an effective treatment for neurogenic cough based on existing retrospective data. This will be achieved through the design of a prospective, single-blind, randomized clinical trial in which one group of patients will undergo a series of two standard (steroid-lidocaine mixture) injections and the second group will undergo a series of two placebo (saline) injections. By determining if a clinically significant difference exists between the outcomes of the two groups, measured by a dichotomous yes/no response to improvement, the Leicester Cough Questionnaire, and a visual analogue scale for symptom severity. This will provide the answer to the general question of whether or not these injections are clinically effective for patients with neurogenic cough. Furthermore, any adverse reactions will be thoroughly documented. The significance of this specific aim is to confirm the clinical utility of superior laryngeal nerve blocks; if proven effective, this can greatly improve the care of these patients by allowing for an evidence-based treatment option.

Given the focus and timeframe of the proposed project, this one aim to determine overall efficacy is sufficient; however, it could be further subdivided:

**Aim 1a:** Determine if patients who undergo a series of superior laryngeal nerve blocks report improvement in cough severity and quality of life.

**Aim 1b:** Determine the placebo effect of superior laryngeal nerve blocks in the treatment of neurogenic chronic cough.

**Aim 1c:** Determine the average amount of time post-injection at which symptoms return.

**Aim 1d:** Determine the rate of complications of in-office superior laryngeal nerve blocks.

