### **Figure 2. Flow Diagram of Study Design**

Injection will be completed near the lateral thyrohyoid membrane by a single experienced laryngologist per previously published methodology utilizing bony, soft tissue and cartilaginous landmarks. An illustration of the anatomic target for the injection can be seen in Figure 3. To minimize patient discomfort, lidocaine cream will be applied to the skin prior to injections.

Following injection, patients will be instructed to follow up in a 2- to 3-week time frame; however, we will include all patients in analysis if they follow up within 1-4 weeks. Any follow up outside of that window will lead to removal of the patient's data from the analysis. At follow up, if the patient's cough has improved by greater than or equal to 50% compared to baseline, we will repeat the injection on the same side. If less than 50%, we will move to the other side to perform the injection. Patients will undergo a total of two injections before data collection is complete for analysis. If patients were to experience full resolution of cough (i.e. report 0/10 for cough severity) after the first injection alone, then at that point, their condition would be considered cured and their enrollment in the study will finish. The reason for this is to avoid unnecessary and unindicated injections in patients with resolution of cough.

2 weeks after the second injection, participants will be unblinded. If in the placebo group, they will have the opportunity to complete 2 additional treatment injections (unblinded) under the study protocol. Data will be collected and stored in the same fashion as prior to unblinding.

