## 12.0 Data Management

Descriptional analysis of all demographic data, including sex and age, will be completed. Dichotomous data will be summarized as percentages per group per injection and compared via chi-squared analysis. Changes in Leicester Cough Questionnaire scores, both global and specific domains (physical, psychological and social), will be analyzed via a linear regression model. An independent t-test will then be used to compare both study arms. Regression analysis will also be performed on the data collected from the patient log, specifically the daily visual analogue scale. A ruler will be used to the identify the exact percentage along the scale that represents the patient's cough severity. A comprehensive compilation of side effects reported by the treatment group will be reported as a proportion of the total number of patients in the treatment study arm (n = 25) and compared to the placebo group (n=25). The data collected from the placebo group pre-unblinding will be directly compared to the results achieved from treatment injections offered following unblinding.

Data will not leave MUSC. Patient identifiers (MRN) will be kept coded on a separate, password-protected file stored on a secure drive.

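### The follow-up window rule has no exception for safety data, while side effects are reported over a fixed 25 per arm; read together, the two rules understate the side-effect rate

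*Combined protocol and SAP*

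**What the plan says.** Section 10.0, in the text after the Figure 2 caption, asks patients to return 2 to 3 weeks after injection and sets a wider window for the analysis: "we will include all patients in analysis if they follow up within 1-4 weeks". The next sentence reads: "Any follow up outside of that window will lead to removal of the patient's data from the analysis". It does not distinguish efficacy data from safety data.

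Section 12.0 describes the safety summary. It starts from "A comprehensive compilation of side effects reported by the treatment group", which is to be "reported as a proportion of the total number of patients in the treatment study arm (n = 25"). The placebo arm serves as comparator, with the same denominator of 25.

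The side-effect and complication rate is the secondary endpoint in Section 4.0 and has its own aim in Section 1.0, Aim 1d: "Determine the rate of complications of in-office superior laryngeal nerve blocks". No section defines a safety population or says how side effects in removed patients are counted.

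**The concern.** The removal rule acts on all of a patient's data, but the safety denominator is printed as the full arm. If an analyst applies both as written, a patient who was injected, had a side effect and returned outside the window still counts among the 25, but as someone without a side effect. The error runs one way: the reported rate can only fall.

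At stake is one of the questions the trial is meant to answer. Section 2.0 says that safety remains an open question, and Aim 1d asks for a complication rate. With 25 patients per arm, a single lost case changes the result visibly. If a side effect itself makes a late return more likely, the loss falls on exactly the patients the summary should count. The documents do not say whether this happens.

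**Working it through.** **Inputs**

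- Denominator: 25 per arm (Section 12.0; Section 10.0 has 25 cards for each arm).
- Illustrative rate: 4 of 23 patients with self-limited globus in the site's own series (Section 2.0). This is the only numerical side-effect rate for the injections in the documents.
- Number removed per arm, *d*: not given. I use 0 to 7 as an assumed range. Its upper end is where 25 falls to the 18 per group that Section 6.0 says are needed (25 − 18 = 7).

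**The plan's own figure.** 4/23 = 17.4%, which agrees with the printed 17%. Over 25 patients this is 0.174 × 25 = 4.3, or about 4 patients.

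**Case 1: the removed patient had a side effect.** The reported rate is (patients with a side effect who are retained)/25. Each loss costs 1/25 = 4 percentage points.

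- None removed: 4/25 = 16%
- One removed: 3/25 = 12%

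Taking the patient out of the denominator as well does not repair this: 3/24 = 12.5%, still below 16%.

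**Case 2: removal is unrelated to side effects.** If the true rate is *r*, the expected reported rate is *r* × (25 − *d*)/25 = *r* × (1 − *d*/25). With *r* = 17.4%:

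| *d* removed | Factor 1 − *d*/25 | Reported rate |
|---|---|---|
| 0 | 1.00 | 17.4% |
| 2 | 0.92 | 16.0% |
| 3 | 0.88 | 15.3% |
| 5 | 0.80 | 13.9% |
| 7 | 0.72 | 12.5% |

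Here a denominator of 25 − *d* would restore the expected rate, because *r*(25 − *d*)/(25 − *d*) = *r*. It would not do so in Case 1. Summarising all injected patients avoids the removal loss in both cases.

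**Comparison between arms.** If the same *d* applies to both arms under Case 2, both rates, and so their difference, shrink by 1 − *d*/25. If removal differs between arms, the documents give no basis for stating the size or direction of the bias.

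**The case against.** The strongest reply is that Section 12.0 is the only text on how side effects are summarised, and that it points to all-patient reporting. It calls the compilation comprehensive and divides by the total in the arm. On that view the printed 25 shows that the window rule was never meant to reach safety data. The rule also stands among efficacy steps, next to the assessment of percentage improvement. This stands as a fair reading, so the loss from the numerator is not certain. It does not remove the problem: the rule in Section 10.0 is unqualified, and two careful analysts could report different rates from the same data.

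A reader might also infer several stronger points that the documents do not support.

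- **That the rule breaks the promise in Section 1.0.** The promise is that "any adverse reactions will be thoroughly documented". Removal from the analysis is not removal from the record. The patient log, its review at least every 4 weeks and the direct line in Section 13.0 all continue.
- **That a serious event could vanish, turning 1/25 into 0/25.** Section 13.0 sends serious events to the IRB immediately and ends the study, and Section 15.0 repeats the early termination.
- **That patients who never return are covered by the same sentence.** It concerns follow-up outside the window. Never-returners drop out only by implication of the sentence before it, and if their logs do not come back, that is a gap in data collection.
- **That an unscheduled visit before one week removes the patient.** Nothing says that such a visit replaces the planned one; the patient can still attend within the window.
- **That most affected patients would be lost.** Globus is described as self-limited, and nothing suggests that it disturbs the visit schedule. Losing two or three of four cases is not a forecast that the documents support.

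**Conclusion.** The concern holds as a conflict between two sections, with a known direction of error if the Section 10.0 rule is applied as written. The side-effect rate is then understated by 4 percentage points for each removed patient who had a side effect. If removal is unrelated to side effects, it is understated by the factor 1 − *d*/25.

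The size rests on two assumptions: that the site's globus rate is a usable guide to the side-effect rate in the active arm, and the value of *d*. For two to five removals per arm the loss in Case 2 is about 1.4 to 3.5 percentage points (17.4 − 16.0 and 17.4 − 13.9). The effect is confined to the reported summary of mainly non-serious events. It does not mean that safety goes unmonitored, nor does it show that the treatment will be made to look safer than placebo. Because the figure is a stated secondary endpoint and the repair is nearly free, the wording should be settled before the data are analysed.

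**What to change.** Two changes of wording:

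1. In Section 10.0, limit the window rule to efficacy data.
2. In Section 12.0, state that side effects are summarised by arm for every patient who received an injection, whatever the timing of follow-up, using reports already collected (log, visits and direct line). Give the number injected as the denominator, and report how many injected patients in each arm have no safety follow-up.

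The last count matters because wording cannot recover side effects that were never reported; it lets the reader see how many patients in the denominator have unknown status.

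The cost is a couple of sentences and one extra count, with no new data collection and no effect on the efficacy analysis. The one downside for the sponsor is that the reported side-effect rate may be slightly less favourable.

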## **6.0 Number of Subjects**

We will recruit 50 patients. Our institution has several otolaryngologists who routinely treat chronic cough and, within the past year, a single provider performed superior laryngeal nerve blocks on 29 patients, with the majority of the injections occurring within the last 2-3 months. Therefore, we are confident in our ability to recruit 50 patients within 1 year. Assuming a dichotomous outcome of >50% improvement or not, a 70% treatment effect, a 25% possible incidence of improvement in placebo, and an 80% confidence level, we would need 18 patients in each group (total N=36) to power our study.

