**Figure 3. Anatomic Target of Superior Laryngeal Nerve Blocks.**

During the procedure, the thyroid cartilage, hyoid, and thyrohyoid membrane are palpated as key anatomic landmarks. The target of the injection, the superior laryngeal nerve, pierces the thyrohyoid membrane superior to the superior laryngeal artery. The plunger is drawn back prior to injection to ensure needle tip is not intravascular. Illustration by author.

Patients will be provided a log to track their progress throughout treatment. This will include a visual analogue scale to be completed daily after each injection to document cough severity, as well as opportunities to document any adverse effects or general comments. An example of this log can be seen in Figure 4. At each follow up visit, patients will provide a dichotomous answer (Yes or No) if they experienced improvement in cough and will disclose how long the improvement lasted. They will also fill out the Leicester Cough Questionnaire (LCQ), a validated 19-question quality of life survey for chronic cough. The LCQ will be the study's primary outcome measure. Please see Appendix 1 for a copy of the Leicester Cough Questionnaire. After the last injection, patients will return to the clinic in three months or opt to be contacted via telephone to assess if symptoms have returned.

Date of last injection: _____
 
WEEK 1  Please mark on the line below with a "X" how severe you believe your cough is. The far left indicates no cough at all, and the far right is indicative of the most severe cough.
 
Day 1 no cough ..... severe cough
 
Day 2 no cough ..... severe cough
 
Day 3 no cough ..... severe cough
 
Day 4 no cough ..... severe cough
 
Day 5 no cough ..... severe cough
 
Day 6 no cough ..... severe cough
 
Day 7 no cough ..... severe cough
	

Date of last injection: _____
 
WEEK 2  Please mark on the line below with a "X" how severe you believe your cough is. The far left indicates no cough at all, and the far right is indicative of the most severe cough.
 
Day 1 no cough ..... severe cough
 
Day 2 no cough ..... severe cough
 
Day 3 no cough ..... severe cough
 
Day 4 no cough ..... severe cough
 
Day 5 no cough ..... severe cough
 
Day 6 no cough ..... severe cough
 
Day 7 no cough ..... severe cough
	

Any side effects?
	
Any side effects?

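### Patients reporting 0/10 cough after the first injection leave the study instead of only skipping the second injection, so their later outcomes go unrecorded; the size is unknown but the remedy is cheap

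*Combined protocol and SAP*

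**What the plan says.** The exit rule is in section 10.0, in the text after the Figure 2 caption. A patient with full resolution (0/10) after one injection is covered by "then at that point, their condition would be considered cured and their enrollment in the study will finish". The reason follows at once: "The reason for this is to avoid unnecessary and unindicated injections in patients with resolution of cough".

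Four other statements bear on it:

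- Same text, on when analysis data are complete: "Patients will undergo a total of two injections before data collection is complete for analysis".
- Same text, on visits outside 1 to 4 weeks after injection: "Any follow up outside of that window will lead to removal of the patient's data from the analysis".
- Same text, on unblinding: "2 weeks after the second injection, participants will be unblinded".
- Section 10.0, after the Figure 3 caption, on later follow-up: "After the last injection, patients will return to the clinic in three months or opt to be contacted via telephone", the purpose being to learn whether symptoms have come back.

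Section 12.0 plans the binary analysis: "Dichotomous data will be summarized as percentages per group per injection and compared via chi-squared analysis". The Leicester Cough Questionnaire (LCQ), the primary outcome, is completed at each follow-up visit. No primary time point is stated for it. Aim 1c in section 1.0 is the average time to symptom return.

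**The concern.** The rule goes further than its reason. Avoiding an injection requires only that the injection be withheld; it does not require that outcome collection stop.

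Patients who exit contribute an LCQ and a yes/no answer after the first injection and nothing after that. Yet a comparison after the second injection is planned, at least for the yes/no outcome. The exit trigger is the best possible response, so the missing values depend on outcome. A comparison of those who remain is then no longer a comparison of the randomised groups.

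No visible text says whether these patients are dropped, counted as responders, or represented by their first-visit values. That choice would be made after the results are known. Aim 1c has a separate problem: whether a patient declared cured later relapses may never be recorded.

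**Working it through.** **The plan's own figure.** Section 6.0 states: "Assuming a dichotomous outcome of >50% improvement or not, a 70% treatment effect, a 25% possible incidence of improvement in placebo", and arrives at 18 per group. I read 70% as the active response rate and the 80% figure as power, and I assume a two-sided 0.05 test, since no alpha is given. The arcsine formula has h = 2·asin(√0.70) − 2·asin(√0.25) = 0.935. Then n = 2(1.960 + 0.842)²/h² = 17.95, which rounds up to 18. The pooled normal formula gives 19. The 70% v 25% reading is therefore a fair basis for illustration.

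**Yes/no outcome if exits are dropped.** Inputs are 25 per arm (section 12.0) and the 70% and 25% rates (section 6.0). Those rates are defined there as more than 50% improvement and are borrowed here for the yes/no question. I assume every exit would have remained a 'yes'. Expected responders are 17.5 and 6.25. With a active and b placebo exits, the observed rates are (17.5 − a)/(25 − a) and (6.25 − b)/(25 − b).

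| Exits, active v placebo | Active | Placebo | Difference (points) |
|---|---|---|---|
| 0 v 0 | 70.0% | 25.0% | 45.0 |
| 1 v 0 | 68.8% | 25.0% | 43.8 |
| 3 v 0 | 65.9% | 25.0% | 40.9 |
| 1 v 1 | 68.8% | 21.9% | 46.9 |
| 2 v 1 | 67.4% | 21.9% | 45.5 |
| 3 v 1 | 65.9% | 21.9% | 44.0 |
| 3 v 2 | 65.9% | 18.5% | 47.4 |

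The direction changes because removing one responder lowers a rate p by (1 − p)/(n − 1). In the active arm that is 0.30/24 = 1.25 points; in the placebo arm it is 0.75/24 = 3.13 points. One placebo exit therefore outweighs two active exits, and with one placebo exit it takes three active exits before the difference shrinks.

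**LCQ if exits are dropped.** This is an illustration under assumptions, not an estimate. Take a true benefit d = 0.8 SD, 25 per arm, exit when the first-visit improvement exceeds a threshold c, and correlation r between that improvement and the later LCQ. The observed difference is d − r·[φ(c−d)/Φ(c−d) − φ(c)/Φ(c)].

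- c = 2.85 (exits 2.0% v 0.2%): 0.789 at r = 0.25 and 0.766 at r = 0.8, so 1.3% to 4.3% too small.
- c = 2.5 (exits 4.5% v 0.6%, about 1 patient v 0): 0.780 and 0.735, so 2.5% to 8.1% too small.

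Simulated power (two-sided t-test at 0.05, 40,000 trials) is about 79% with everyone retained, about 77–78% in the first case and 74–77% in the second.

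**First-visit LCQ carried forward.** If the first-visit LCQ correlates with the exit trigger more strongly than the later LCQ does, by g, the difference becomes d + g·[φ(c−d) − φ(c)]. At c = 2.85 with assumed g of 0.1 to 0.3 this is 0.804 to 0.813, or 0.5% to 1.6% too large. Relief that truly fades between visits could add to that.

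**Three-month contact.** If it covers patients with only one injection, it follows people whose enrolment has ended, contrary to the exit rule. If it covers only those still enrolled, Aim 1c loses the complete responders. The two statements must be reconciled on either reading.

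**The case against.** The strongest reply is that nothing here shows a bias of any size. No document gives the share reaching 0/10 after one injection. Section 2.0 reports average scores well above zero after an average of 2.4 blocks (cough severity index 26.8 to 14.6) and of 3.8 blocks (Hull questionnaire 38 to 23). That makes complete resolution after one injection look uncommon, though averages do not give a rate, and in the investigators' own series the largest severity change followed the first injection. This point stands.

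The LCQ model is also only an analogy. The rule is triggered by an absolute score of 0/10, not by the amount of improvement, so a patient with mild baseline cough could exit after a small change. The correlations have no source. This stands too, and it is why those percentages are not estimates for this trial.

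Dropping these patients is not stated either. Describing them as cured would fit counting them as responders, and an LCQ analysis set after the first injection would not be touched. That is fair: loss of data is what the text says, while bias depends on a choice the text leaves open.

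Finally, ending enrolment might mean only the end of the injection phase. Section 17.0 places study completion at the three-month follow-up, and the Figure 2 flow diagram is not available to check. That reading is possible, but the words used are about study enrolment, and one clarifying sentence would settle it.

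A reader might infer that the rule biases the trial towards no effect. The documents do not support this. The yes/no difference widens when exits are similar between arms, and even at 2 v 1.

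**Conclusion.** The concern holds as a cheap improvement, not as a demonstrated bias. The exit rule exceeds its stated reason. Followed as written, it leaves the most complete first-injection responses without outcomes at the post-injection-2 time point and probably without relapse data.

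If these patients are dropped, the yes/no difference shrinks when exits are much commoner in the active arm (43.8 points at 1 v 0) and grows when exits are similar (46.9 at 1 v 1), against 45 undropped. Carrying first-visit values forward may overstate benefit if relief fades. These figures rest on section 6.0's rates, 25 per arm, and exits who would have stayed responders.

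The true size is unknown and may be negligible. The post-injection-1 comparison is unaffected, so it would be wrong to conclude that the primary result is compromised: the LCQ has no stated primary time point, and the handling of these patients is not stated. Because neither size nor direction can be known beforehand, the sensible course is to collect the data and fix the handling in advance.

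**What to change.** Leave the rule on withholding the second injection unchanged, and separate it from follow-up.

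- **Section 10.0, exit rule.** Replace the ending of enrolment with wording such as: *they receive no second injection but remain in the study, and complete the LCQ, yes/no response and VAS log on the schedule used after a second injection; for them the 1–4 week window is counted from the visit at which that injection would have been given.* The last clause is needed. A first visit at 2–3 weeks plus a further 2–3 weeks puts the added visit 4–6 weeks after their only injection, where the window rule could delete it.
- **Section 10.0, three-month contact.** State that it applies to all randomised patients, including those who had one injection.
- **Section 12.0.** State that these patients are analysed in their assigned arm at the post-injection-2 time point using observed values, with first-visit values carried forward only as a sensitivity analysis when the later value is missing.
- **Unblinding.** It is timed from a second injection that these patients do not receive; reconcile the two.

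The cost is a few sentences and, for a few patients, one extra visit or call, one questionnaire, one log and the three-month contact. No injection is added, and all the instruments are already in the plan.

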## **10.0 Study Design / Methods**

Figure 2 depicts the flow diagram of the study design. Once patients have met inclusion and exclusion criteria (including undergoing all diagnostic testing for other potential causes of chronic cough) and have agreed to study participation, informed consent will be obtained and they will be randomized into two groups: treatment and placebo. This will be achieved using randomly-assorted, secured envelopes containing a card indicating whether the patient will be in the treatment or placebo group. This will be unveiled immediately to the provider administering the first injection, but remain unknown to the subject. There will be 25 "Treatment" and 25 "Placebo" cards within the 50, individually-secured envelopes. On initial visit, prior to the injection, patients will first undergo nasal laryngoscopy as part of standard of care. If there is any vocal fold weakness seen on scope examination or if there is a unilateral trigger point identified, then the first injection will start on the side of the suspected neuropathy. If there is no evidence of neuropathy on examination, we will start with a left-sided injection. Injections will be standardized to 2 mL of a 1:1 triamcinolone 40mg: 1% lidocaine with 1:200,000 epinephrine. Injection syringe will be brought into room by the physician in an opaque box and placed behind patient so they cannot view the syringe prior to injection. During the injection, a paper "shield" will be held under the patient's chin by an assistant and they will be asked to close their eyes so that they are not able to view the syringe during injection. This is necessary as steroid possesses a white color as compared to clear saline. The practitioner is not blinded so that proper drawing back on the syringe is not compromised to avoid intravascular or airway injection.

[figure not shown]

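### Participants are unblinded on a fixed date after the second injection, not once the LCQ and yes/no response are in, so blinded rating of the primary outcome is intended but not secured

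*Combined protocol and SAP*

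**What the plan says.** All of the relevant timing is in Section 10.0 (Study Design / Methods).

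- **Who is blinded.** The trial is single-blind. Of the allocation card the plan says: "This will be unveiled immediately to the provider administering the first injection, but remain unknown to the subject".
- **Follow-up window.** After injection, patients are told to return in 2 to 3 weeks. For analysis the limit is wider: "we will include all patients in analysis if they follow up within 1-4 weeks". Data from visits outside that range are removed.
- **What is rated, and when.** "At each follow up visit, patients will provide a dichotomous answer (Yes or No) if they experienced improvement in cough". Of the same visits it says: "They will also fill out the Leicester Cough Questionnaire (LCQ), a validated 19-question quality of life survey for chronic cough". It adds: "The LCQ will be the study's primary outcome measure".
- **End of the randomised phase.** "Patients will undergo a total of two injections before data collection is complete for analysis".
- **Unblinding.** "2 weeks after the second injection, participants will be unblinded". Placebo participants may then have two open treatment injections, and of this later phase the plan says: "Data will be collected and stored in the same fashion as prior to unblinding".

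Section 12.0 (Data Management) plans to compare the placebo group's results from before unblinding with those from the open injections.

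**The concern.** Disclosure is set by the calendar, while the ratings are set by visits whose dates can vary. Nothing in the readable text makes one wait for the other, so the rating after the second injection could be made by a patient who already knows the arm.

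Patient blinding is the main protection for these outcomes. The provider knows the allocation from the first injection, and both the LCQ and the yes/no response are the patient's own report. The plan works to keep the patient blind during the procedure, with a hidden syringe, a paper shield and closed eyes. A disclosure step with no fixed place in the sequence can undo that work.

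The rating after the second injection matters because the intervention is defined as a two-injection series (Section 1.0), and because Section 12.0 summarises the dichotomous response per injection. Aim 1b is to measure the placebo effect. A rating made with the allocation known mixes expectation with drug effect, which is what the placebo arm is there to separate.

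**Working it through.** The plan gives no figure on this point to reproduce. The check compares the timing statements, counting days from the second injection.

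**Inputs (all from Section 10.0)**

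| Item | Stated | In days |
|---|---|---|
| Unblinding | 2 weeks after second injection | 14 |
| Instructed follow-up | 2 to 3 weeks after injection | 14 to 21 |
| Follow-up accepted for analysis | 1 to 4 weeks | 7 to 28 |
| LCQ and yes/no response | at each follow-up visit | day of visit |

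**Step 1. Does the window apply after the second injection?** The text does not settle this. The window is introduced for follow-up after injection in general. The sentences that come next, however, describe the visit at which the second injection is given. No other window is stated. The only other contact described after the last injection is at three months, well after unblinding. Two readings are therefore open.

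**Step 2. Reading A: the window applies, and disclosure is made on day 14 as written.** The longest interval from disclosure to rating is the last permitted visit day minus the disclosure day:

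- instructed window: 21 − 14 = 7 days
- accepted window: 28 − 14 = 14 days

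Day 14 is the first day of the instructed window. A patient who follows instructions and attends on any of days 15 to 21 would rate after disclosure. So would one who attends on days 22 to 28, and both would be analysed.

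**Step 3. Reading B: the 2-week point is the closing visit.** No separate unblinding contact is described, which supports this reading. The interval is 14 − 14 = 0 days. What remains unstated is whether the questionnaires are completed before or after the patient is told.

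**Step 4. Does any text fix the order?** Three statements bear on it:

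- The sentence that data collection for analysis is complete after two injections does not mention disclosure.
- "Data will be collected and stored in the same fashion as prior to unblinding" implies that there were data before unblinding, but does not say that every post-second-injection rating is among them.
- The Section 12.0 comparison treats the placebo data as gathered before unblinding. It covers only that group and sets no procedure.

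All three point to blinded collection as the intention; none requires it.

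**Step 5. What is not affected.** The LCQ and yes/no response after the first injection come before any disclosure. The example symptom log runs for two weeks, so the daily visual analogue ratings fall largely before day 14.

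**Step 6. Size of bias.** An estimate needs the share of ratings made after disclosure and the shift that disclosure causes. The documents give neither, so none is computed.

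**The case against.** The strongest reply is that Reading B is the simpler one. Section 10.0 moves from completed data collection, to unblinding at 2 weeks, to the offer of open injections. The example log covers two weeks, which fits a 2-week close. No telephone or postal disclosure is described; the only telephone contact is at three months. Harm under Reading A needs both the general window to govern this visit and disclosure to occur before the patient attends. Placebo data described as gathered before unblinding would not fit with ratings made afterwards. Figure 2, which depicts the study flow, could not be seen and may give the order. On this view the gap is a drafting detail, limited at worst to later attenders after the second injection, with no bias shown.

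Much of this stands. The intention is clear, Reading B is plausible, the first-injection ratings are safe, and the diagram might resolve the matter. It would be wrong to say that the ratings are made unblinded.

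It does not remove the point. Staff who follow the sentence literally could disclose on day 14 to a patient due on day 18 and break no stated rule. Even under Reading B the order within the visit is left to chance. An intention to rate blind does not amount to a procedure.

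**Conclusion.** The concern holds as a limited claim: blinded rating of the LCQ and yes/no response after the second injection is intended but not secured. The exposure can be stated only as time. It is up to 14 days between disclosure and an analysable rating if the 1 to 4 week window applies after the second injection, up to 7 days within the instructed window, and 0 days with the order unstated if disclosure takes place at the closing visit.

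This rests on two assumptions: that the 2-week trigger would be applied as written, and that the unseen Figure 2 does not fix the sequence. Confidence is medium for that reason. The point should be fixed because the patient is both the blinded party and the rater, and the correction is cheap.

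**What to change.** Replace the calendar trigger with a conditional one, for example:

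> Allocation will be disclosed only after the post-second-injection LCQ, yes/no response and symptom log have been collected, or once the accepted follow-up window has closed without a visit.

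Add one sentence stating which follow-up window applies after the second injection. The sponsor should then reconcile the Section 10.0 text on unblinding and the open injections with that order, and check Figure 2 against it.

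The cost is one replaced sentence and one added sentence, with no extra visit, staff or patients. If the 1 to 4 week window applies, some participants would learn their allocation, and placebo participants would be offered the open injections, up to about 2 weeks later (28 − 14 = 14 days). If the 2-week point is already the closing visit, patients who attend it face no delay.
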